6.2 Dose Modification

6.2.1 Dose-cohort Study Escalation/De-escalation and Stopping Rules

Dose Level Determination

A recommendation to escalate to a higher dose cohort will only occur when the previous dose regimen(s) have been found to be reasonably well tolerated based on available study data through study day 15 for a minimum of 7 out of 8 dosed subjects (cohorts 1 to 6 and cohort 11) or through study day 36 for 6 of 8 dosed subjects (cohorts 7 to 10) and upon unanimous agreement of the DLRT members. Available data from previous cohorts will also be considered. Dose level recommendations will be made on a treatment cohort basis (not on an individual basis). After receiving the DLRT recommendation, Amgen will render a final decision and will issue a written notification of the dose change decision to investigators. **The DLRT will not make a dose level recommendation after reviewing the safety and tolerability data through study day 36 for subjects in cohorts 12 to 13 as these are terminal cohorts.** Further information on DLRMs is provided in Appendix 3 (Section 11.3).

Dose Cohort Stopping Rules

The DLRT will recommend stopping or modifying dosing if suspected adverse drug reactions, changes in vital signs, ECG, or clinical laboratory results are observed and these changes pose a significant health risk. In addition, dosing will be stopped or modified if any of the stopping rules shown in [Table 11](#) are met. The Amgen medical monitor may suspend dosing and convene a DLRM at any time based on emerging safety data.

Dosing will be stopped or modified as shown in [Table 11](#).

Table 11. Dose Cohort Stopping Rules

Scenario	Action

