Any occurrence of an Amgen Standard Grading Scale moderate adverse event of similar type in 2 or more subjects in the same cohort.	
Stop dosing and convene DLRM (if event occurs outside the regularly scheduled DLRM).
 
Review adverse event and all relevant safety data for evidence of relationship to treatment and clinical or medical significance.
 
Consider unblinding, as appropriate.^a
 
Based on the DLRM vote, 1 of the following recommendations may be made:
 
• stop enrollment of the cohort (if applicable)• resume enrollment of the cohort as planned• expand the cohort at the same dose• continue enrollment of the study at a lower dose• upon a unanimous vote escalate to an intermediate dose (a dose lower than the next planned dose)• upon a unanimous vote escalate to the next planned dose
Any occurrence of an Amgen Standard Grading Scale severe adverse event.	
Stop dosing additional subjects in the cohort and convene DLRM (if the event occurs outside the regularly scheduled DLRM).
 
Review adverse event and all relevant safety data for evidence of relationship to treatment and clinical or medical significance.
 
Consider unblinding to determine relatedness to investigational product.^a
 
If the adverse event is determined by a majority vote of the DLRT to be related to study drug and clinically or medically significant, recommend that no further doses should be administered at this dose and no dose escalation should proceed. Recommend that enrollment of the study continue at a lower dose or a lower dose cohort may be added to the study.
 
Otherwise, based on the majority vote of the DLRT, 1 of the following recommendations may be made:
 
• resume enrollment of the cohort as planned• expand the cohort at the same dose• continue enrollment of the study at a lower dose or add a lower dose cohort to the study.

DLRM = dose level review meeting; DLRT = dose level review team

^a A subject's treatment assignment should only be unblinded when knowledge of the treatment is essential for the further management of the subject or may impact the safety of subjects currently enrolled or of subjects in subsequent cohorts.

Clinically or medically significant serious adverse events and suspected adverse drug reactions considered to be related to study procedures will be followed until resolved or considered stable.

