8.2.3.1.2 Serious Adverse Events

The investigator is responsible for ensuring that all serious adverse events observed by the investigator or reported by the subject that occur after signing of the informed consent through 30 (+3) days of last dose of investigational product or end of study, whichever is later are reported using the Events CRF.

All serious adverse events will be collected, recorded and reported to the sponsor or designee within 24 hours of the investigator's awareness of the event, as indicated in Section 11.4. The investigator will submit any updated serious adverse event data to the sponsor within 24 hours of it being available.

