11.3 Appendix 3. Study Governance Considerations

Dose Level Review Meetings (DLRM)

A DLRM is conducted to review and interpret safety data for the purposes of making recommendations about dose-level escalation (either to the next planned dose or to an intermediate dose), dose level de-escalation, cohort continuation, or cohort expansion; making recommendations about non-dose escalation cohorts (eg, expanded, highest dose and/or final cohort); and evaluating safety signals for purposes of applying Dose Cohort Stopping Rules. The required Dose Level Review Team (DLRT) members are the medical monitor, Global Safety Officer (GSO), and Site Investigators. The DLRT will include actively screening and enrolling Site Investigators. The medical monitor, GSO, and Site Investigators are the only voting DLRT members. The following nonvoting Amgen representatives may also be part of the DLRT: clinical study manager, biostatistician, or pharmacokinetics scientist.

The medical monitor must be in attendance and cannot be represented by a voting designee or delegate. Voting designees can be identified as appropriate by the GSO or site investigator(s). A site investigator may identify a delegate (eg, sub-investigator) who is listed in the Delegation of Authority. If a site investigator does this, the site investigator must provide written agreement with the designee or delegate's vote.

For a DLRM to occur, the medical monitor must attend, and the GSO or delegate must attend. In addition, a quorum of Site Investigators must be present. A quorum is defined as more than 50% of the participating investigators or their qualified designees. The DLRM will be rescheduled if these requirements are not met.

All available study data, including demographics, investigational product administration, medical history, concomitant medications, adverse events, electrocardiogram (ECG), vital signs, and laboratory results will be reviewed. Data to be reviewed will be unqueried.

Data will be reviewed blinded (ie, treatment assignment will not be revealed) unless unblinding is deemed necessary for the review team to make dosing recommendations. If deemed necessary, unblinding will be performed to assist dose change recommendations, in accordance with Amgen standard procedures.

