
When an adverse event or serious adverse event occurs, it is the responsibility of the investigator to review all documentation (eg, hospital progress notes, laboratory, and diagnostics reports) related to the event.The investigator will then record all relevant adverse event/serious adverse event information in the event case report form (CRF).The investigator must assign the following adverse event attributes:
Adverse event diagnosis or syndrome(s), if known (if not known, signs or symptoms);Dates of onset and resolution (if resolved);Did the event start prior to first dose of investigational product, other protocol-required therapies;Assessment of seriousness;Severity (or toxicity defined below);Assessment of relatedness to investigational product, study-mandated procedures, and protocol-provided therapies; and/or study-mandated activity and/or procedures;Action taken; andOutcome of event.If the severity of an adverse event worsens from the date of onset to the date of resolution, record a single event for each increased level of severity on the Event CRF.It is not acceptable for the investigator to send photocopies of the subject's medical records to sponsor/responsible contact research organization in lieu of completion of the Event CRF page.If specifically requested, the investigator may need to provide additional follow-up information, such as discharge summaries, medical records, or extracts from the medical records. In this case, all subject identifiers, with the exception of the subject number, will be blinded on the copies of the medical records before submission to Amgen.The investigator will attempt to establish a diagnosis of the event based on signs, symptoms, and/or other clinical information. In such cases, the diagnosis (not the individual signs/symptoms) will be documented as the adverse event/serious adverse event.

Evaluating Adverse Events and Serious Adverse Events

Assessment of Severity	
The investigator will make an assessment of severity for each adverse event and serious adverse event reported during the study. The assessment of severity will be based on:	
The Amgen Standard Grading Scale as show below:	
Grade	Definition
MILD	Aware of sign or symptom, but easily tolerated
MODERATE	Discomfort enough to cause interference with usual activity

SEVERE ^a	Incapacitating with inability to work or do usual activity

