^a An event is defined as 'serious' when it meets at least 1 of the predefined outcomes as described in the definition of a serious adverse event, NOT when it is rated as severe.	
Assessment of Causality	

• The investigator is obligated to assess the relationship between investigational product, study-mandated procedure, and/or protocol-mandated therapies and each occurrence of each adverse event/serious adverse event.• Relatedness means that there are facts or reasons to support a relationship between investigational product and the event.• The investigator will use clinical judgment to determine the relationship.• Alternative causes, such as underlying disease(s), concomitant therapy, and other risk factors, as well as the temporal relationship of the event to study treatment administration will be considered and investigated.• The investigator will also consult the investigator's brochure and/or Product Information, for marketed products, in his/her assessment.• For each adverse event/serious adverse event, the investigator must document in the medical notes that he/she has reviewed the adverse event/serious adverse event and has provided an assessment of causality.• There may be situations in which a serious adverse event has occurred and the investigator has minimal information to include in the initial report. However, it is very important that the investigator always make an assessment of causality for every event before the initial transmission of the serious adverse event data.• The investigator may change his/her opinion of causality in light of follow-up information and send a serious adverse event follow-up report with the updated causality assessment.• The causality assessment is 1 of the criteria used when determining regulatory reporting requirements.	
Follow-up of Adverse Event and Serious Adverse Event	

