To facilitate appropriate monitoring for signals of DILI, cases of concurrent AST or ALT and TBL and/or INR elevation, according to the criteria specified in the above, require the following:

- The event is to be reported to Amgen as a serious adverse event within 24 hours of discovery or notification of the event (ie, before additional etiologic investigations have been concluded)
- The appropriate case report form (CRF) (eg, Event CRF) that captures information necessary to facilitate the evaluation of treatment-emergent liver abnormalities is to be completed and sent to Amgen

Other events of hepatotoxicity and potential DILI are to be reported as serious adverse events if they meet the criteria for a serious adverse event defined in Section 11.4.

Additional Clinical Assessments and Observation

All subjects in whom investigational product(s) or protocol-required therapies is/are withheld (either permanently or conditionally) due to potential DILI as specified in [Table 13](#) or who experience AST or ALT elevations $> 3 \times$ upper limit of normal (ULN) or 2-fold increases above baseline values for subjects with elevated values before drug are to undergo a period of “close observation” until abnormalities return to normal or to the subject’s baseline levels.

Assessments that are to be performed during this period include:

- Repeat AST, ALT, ALP, BIL (total and direct), and INR within 24 hours
- In cases of TBL $> 2 \times$ ULN or INR > 1.5 , retesting of liver tests, BIL (total and direct), and INR is to be performed every 24 hours until laboratory abnormalities improve

Testing frequency of the above laboratory tests may decrease if the abnormalities stabilize or the investigational product(s) or protocol-required therapies has/have been discontinued AND the subject is asymptomatic.

Initiate investigation of alternative causes for elevated AST or ALT and/or elevated TBL.

The following are to be considered depending on the clinical situation:

- Complete blood count with differential to assess for eosinophilia
- Serum total immunoglobulin (Ig)G, anti-nuclear antibody anti-smooth muscle antibody, and liver kidney microsomal antibody-1 to assess for autoimmune hepatitis
- Serum acetaminophen (paracetamol) levels

A more detailed history of:

- Prior and/or concurrent diseases or illness
- Exposure to environmental and/or industrial chemical agents

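### Table 11 has no trigger for seriousness: a single related SAE graded mild or moderate starts no automatic dosing pause

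*Protocol*

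**What the plan says.** Protocol Section 6.2.1 requires dosing to be stopped or modified when a Table 11 rule is met. Table 11 has two rows. The first needs moderate events of similar type in at least two subjects of the same cohort. The second needs one event: "Any occurrence of an Amgen Standard Grading Scale severe adverse event". Neither row mentions seriousness. The only sentence on serious events below the table concerns follow-up until they resolve or stabilise.

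Appendix 4 keeps the two attributes apart. An event is serious when it meets one of the listed outcomes, such as an in-patient stay, "NOT when it is rated as severe". The mild grade is described as "Aware of sign or symptom, but easily tolerated".

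Two other routes to a stop appear in Section 6.2.1. The DLRT is to recommend stopping or modifying dosing for suspected adverse drug reactions and for vital-sign, ECG or laboratory changes, on condition that such "results are observed and these changes pose a significant health risk". In addition, "The Amgen medical monitor may suspend dosing and convene a DLRM at any time based on emerging safety data". Appendix 3 includes among the purposes of a DLRM "evaluating safety signals for purposes of applying Dose Cohort Stopping Rules". Section 8.2.3.1.2 sets the reporting clock: "All serious adverse events will be collected, recorded and reported to the sponsor or designee within 24 hours" of the investigator becoming aware.

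**The concern.** A stopping table is meant to fix in advance which events halt dosing before anyone weighs them. Here two non-serious moderate nausea events in a cohort force a stop, while one related hospitalisation graded moderate does not. No section links the 24-hour SAE report to a pause in dosing the other subjects.

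The case is not artificial. Appendix 7 requires concurrent transaminase and bilirubin or INR elevation to be reported as an SAE "before additional etiologic investigations have been concluded". The grading scale rests on symptoms and interference with activity, so an asymptomatic liver case could be graded mild. Table 13 then stops AMG 133 for that subject only.

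Table 11 is the same for every cohort. Part C is where the gap now has most effect. Section 4.3 says the single-dose cohorts are complete, and Section 2.2.2.4 gives 39 multiple-dose subjects already enrolled, against about 44 planned for Part B. Cohorts 12 and 13 enrol in parallel with no between-cohort gate, and dosing is weekly at first.

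**Working it through.** The plan gives no figure on this point. Its one computed safety figure, in Section 9.2, reproduces: 1 − 0.97^87 = 92.93% and 1 − 0.95^87 = 98.85%, against the stated 92.9% and 98.8%. It has no bearing on the stopping rule.

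**Step 1. Apply Table 11 to one related SAE in a cohort.**

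| Grade of the SAE | Row 1 | Row 2 | Automatic pause |
|---|---|---|---|
| Mild | no | no | no |
| Moderate, no similar moderate event in another subject | no | no | no |
| Moderate, with a similar moderate event in another subject | yes | no | yes |
| Severe | no | yes | yes |

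**Step 2. Part C doses due before day 36.** Dosing days are in the notes to Tables 5 and 6; each cohort has up to 6 subjects.

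- Cohort 12 (Days 1, 8, 15, 43): 3 of 4 doses, so 6 × 3 = 18 of 6 × 4 = 24.
- Cohort 13 (Days 1, 8, 15, 22, 29, 57): 5 of 6 doses, so 6 × 5 = 30 of 6 × 6 = 36.
- Together: 48 of 60 doses (80%).

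The Synopsis (In-House Residency) places the first dose of a stated, redacted level, followed by required overnight observation, on Day 15 for cohort 12 and Day 29 for cohort 13. Taking that as the step-up, the lower starting doses before day 36 number 6 × 2 = 12 in cohort 12 and 6 × 4 = 24 in cohort 13. That is 36 of the 48. The other 12 are half of the 12 × 2 = 24 planned step-up doses.

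**Step 3. Doses that a cohort-level pause would hold.** Assume a full cohort, a same-day start within it, and no use of the judgement routes before day 36. Count doses due before day 36 to the other 5 subjects.

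| Event after the dose on | Case in cohort 13 | Case in cohort 12 |
|---|---|---|
| Day 1 | 5 × 4 = 20 | 5 × 2 = 10 |
| Day 8 | 5 × 3 = 15 | 5 × 1 = 5 |
| Day 15 | 5 × 2 = 10 | 0 |
| Day 22 | 5 × 1 = 5 | 0 |
| Day 29 | 0 | 0 |

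Of the 20, 15 are starting doses (Days 8, 15, 22) and 5 are step-up doses (Day 29). Of the 10, 5 are starting doses (Day 8) and 5 are step-up doses (Day 15).

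**Step 4. Experience to date.** Section 2.2.2.4 gives 57 single-dose and 39 multiple-dose subjects, 96 in all, and Section 4.3 reports no SAEs. If allocation followed 3:1, about 0.75 × 96 = 72 received AMG 133. Zero events in 72 gives a one-sided 95% upper limit of 1 − 0.05^(1/72) = 4.1% for any SAE, related or not and of any grade. The data were blinded and multiple dosing was incomplete. The documents support no rate for related non-severe SAEs, so no probability of meeting the gap is given.

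**The case against.** The strongest reply is that Section 6.2.1 already covers the case. An SAE suspected to be related is a suspected adverse drug reaction, the seriousness criteria largely describe a significant health risk, and the DLRT's duty to recommend a stop or change is worded as mandatory. The sponsor hears within 24 hours and the medical monitor can act the same day. This stands. A reader might infer that dosing would run on unchecked after a related SAE, and the text does not support that. Nor does the sentence saying the DLRT makes no dose level recommendation for cohorts 12 and 13 remove its stopping role; it only reflects that these are terminal cohorts.

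The gap is also narrow. Many hospitalised subjects would meet the severe definition, and row 2 then fires on one event whatever its cause. What remains is mainly a lone moderate related SAE or an asymptomatic Appendix 7 liver case.

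Finally, a new row would also rest on judgement, because the investigator assigns relatedness and may revise it. A reader might suppose that a written trigger makes the pause certain. It does not. It removes one judgement, whether the health risk is significant, and keeps another.

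None of this supplies the missing step. Under the present text the assessment comes first and the pause follows if it is judged warranted; for a serious related event the usual order is the reverse.

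**Conclusion.** The point holds as a modest, inexpensive improvement in subject protection, worth considering. In any cohort, a single related SAE graded mild or moderate starts no automatic pause and is covered only by judgement. The largest number of doses that the added row itself would hold is 20 in cohort 13 or 10 in cohort 12. Those figures assume full cohorts, a same-day start, an event between Days 1 and 8, and nobody using the judgement routes for weeks. The realistic number is lower.

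Two larger figures are tempting. Adding the parallel cohort over the same period gives 20 + (6 × 2) = 32 or 10 + (6 × 4) = 34 doses, but the row would not itself stop the other cohort; that stays with the DLRM. And 80% of doses before day 36 is not 80% of drug exposure. If the redacted levels were 70 mg then 420 mg, the ends of the range in Section 4.3, the share by milligram would be (36 × 70 + 12 × 420) / (36 × 70 + 24 × 420) = 7,560 / 12,600 = 60%.

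The documents do not show whether Part C dosing has finished. If it has, the row matters only for cohorts that are expanded, repeated or added.

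**What to change.** Add a third row to Table 11.

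- **Scenario:** any serious adverse event suspected to be related to investigational product, regardless of severity grade.
- **Action:** stop dosing additional subjects in the cohort, including scheduled repeat doses, and convene a DLRM. For Part C, that DLRM also decides on dosing in the parallel cohort.
- **Exclusion:** events that are SAEs only because they cross an Appendix 8 threshold, namely a PHQ-9 score of 10 or more or a yes to C-SSRS items 1 to 3. These stay under the individual discontinuation rule in Table 14. Do not exclude C-SSRS items 4 and 5 or suicidal behaviour, which Section 8.2.2.2 treats as high risk.

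The change uses the existing 24-hour SAE report and DLRM process. The cost is an occasional unscheduled DLRM and a short dosing pause, including for some liver cases later found unrelated, since those are reported before the work-up is complete. Without the exclusion, one questionnaire score suspected to be related could halt a whole cohort.

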The study may be terminated at any point at the discretion of the sponsor.

Individual Stopping Rules

No individual dose stopping rules will be implemented.

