6.7.2 Concomitant Treatment

Throughout the study, investigators may prescribe any concomitant medications or treatments deemed necessary to provide adequate supportive care except for those listed in Section [6.1.7](#).

Concomitant therapies are to be collected from enrollment through the end of study. For all concomitant therapies, collect therapy name, indication, dose, unit, frequency, route, start date and stop date.

7. Discontinuation Criteria

Subjects have the right to withdraw from investigational product and/or other protocol-required therapies, protocol procedures, or the study as a whole at any time and for any reason without prejudice to their future medical care by the physician or at the institution.

The investigator and/or sponsor can decide to withdraw a subject(s) from investigational product, device, and/or other protocol-required therapies, protocol procedures, or the study as a whole at any time prior to study completion for the reasons listed in Sections [7.1](#), [7.2.1](#), and [7.2.2](#).

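### After one severe adverse event, Table 11's mandatory first action is narrower than after two similar moderate ones and never holds the affected subject's own next dose

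*Protocol*

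**What the plan says.** Table 11 (Protocol Section 6.2.1) has two triggers.

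- **Moderate row** (similar moderate events in at least two subjects of one cohort). The first action is "Stop dosing and convene DLRM (if event occurs outside the regularly scheduled DLRM".
- **Severe row** (any one severe event). The first action is "Stop dosing additional subjects in the cohort and convene DLRM (if the event occurs outside the regularly scheduled DLRM". If the dose level review team (DLRT) then votes by majority that the event is drug-related and clinically or medically significant, it is to "recommend that no further doses should be administered at this dose and no dose escalation should proceed". The sponsor decides after that: "After receiving the DLRT recommendation, Amgen will render a final decision and will issue a written notification of the dose change decision to investigators".

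The text leading into the table says dosing will be stopped or modified when a rule is met, and refers to the table for how. Under Individual Stopping Rules the same section states: "No individual dose stopping rules will be implemented".

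Three general powers exist. Section 6.2.1 provides that "The Amgen medical monitor may suspend dosing and convene a DLRM at any time based on emerging safety data" and that "The study may be terminated at any point at the discretion of the sponsor". The opening of Section 7 adds: "The investigator and/or sponsor can decide to withdraw a subject(s) from investigational product, device, and/or other protocol-required therapies". Subject-level rules appear only for liver findings (Appendix 7) and for suicidality and PHQ-9 scores (Section 8.2.2.2 and Appendix 8).

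**The concern.** Severe is the higher grade in Appendix 4: the subject is incapacitated. One would expect the immediate hold after such an event to be at least as wide as the hold after moderate events. As worded it is narrower, because it reaches only additional subjects, a term the protocol does not define.

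At stake is the time between the event and the DLRT recommendation with the sponsor's decision. If the affected subject's next dose falls in that time, no mandatory text tells the site to withhold it. A dose once given cannot be taken back, and this product has a long half-life. In Part C the next dose may also be larger. Section 4.3 describes escalation from 70 to 420 mg, and the Synopsis requires an overnight stay after the first dose of a (redacted) level on day 15 in cohort 12 and day 29 in cohort 13. Each of those doses comes 7 days after the one before. That these are step-up doses is an inference, since the levels are blacked out.

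**Working it through.** The plan gives no figure on this point, so the check compares wording and counts days.

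**1. What each first action holds**

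| Dose | Moderate row | Severe row, read as subjects not yet dosed | Severe row, read as everyone but the affected subject |
|---|---|---|---|
| First doses of others | held | held | held |
| Repeat doses of others | held | not held | held |
| Affected subject's next dose | held | not held | not held |

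The moderate column takes the instruction at face value. On the first severe reading the gap is widest. Section 4.1 allows a whole Part B cohort to be dosed on one day, after which no undosed subject may be left to hold.

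**2. Whether other mandatory text fills the gap**

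- The text leading into Table 11 points back to the table.
- Section 6.2.1 disclaims individual stopping rules.
- Section 6.2.2.1 only asks for the reason for a dose change to be recorded.
- The liver and mental-health rules cover only those events. Severe vomiting, for example, meets neither unless the liver criteria are also met.
- The ban on further doses in the severe row follows only after a vote.
- Appendix 3 sets attendance and quorum requirements for a DLRM, with rescheduling if they are not met, but no deadline for an unscheduled one.

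**3. Time to the subject's own next dose**

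Dose days come from the notes to Tables 5 and 6 for Part C and from the Synopsis for Part B. Each gap is the next dose day minus the previous dose day.

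| Cohort | Dose days | Gaps (days) | Repeat doses after 7 days |
|---|---|---|---|
| 7 to 10 | 1, 29, 57 | 28, 28 | 0 of 2 |
| 12 | 1, 8, 15, 43 | 7, 7, 28 | 2 of 3 |
| 13 | 1, 8, 15, 22, 29, 57 | 7, 7, 7, 7, 28 | 4 of 5 |

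Part A is single-dose, so no next dose arises.

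**4. Contacts inside the weekly intervals**

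Scheduled visits and calls from day 1 are:

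- cohort 12 (Table 5): days 1, 8, 15, 20, 43, 57, 71, 132 and 193;
- cohort 13 (Table 6): days 1, 8, 15, 22, 29, 34, 57, 64, 85, 146 and 207.

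The number lying strictly between two weekly doses is 0 in both cohort 12 intervals and 0 in all four cohort 13 intervals. All six intervals start on a day when the overnight stay is optional.

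An event that starts and is reported *k* days after a weekly dose leaves 7 − *k* days to the next one. For *k* = 0 to 6 that is 7 down to 1. An event first reported at the next dosing visit leaves 0 days.

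**5. Persistence of a dose (context only)**

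Section 4.3 gives a preliminary half-life of 15 to 20 days. Assuming simple exponential decline, the fraction left after 7 days is 2^(−7/15) = 0.724 to 2^(−7/20) = 0.785, or about 72% to 78%. The conclusion does not depend on this.

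**The case against.** The strongest reply is that this is a deliberate choice. Table 11 contains cohort rules, the protocol says it has no individual ones, and care of the affected subject is left to clinical judgement. Dosing takes place in the clinic after all predose assessments (Section 8.1.2). The investigator can stop product, and adverse event is a listed reason (Section 7.1). Part C subjects may be kept in-house if they report events that interfere with daily activities (Synopsis). An incapacitated subject is unlikely to be dosed. The moderate row does not mention repeat doses either, and its listed outcomes concern enrollment and escalation. Taken as a whole, the severe row is stricter: one event triggers it, and a related and significant event bars both further doses at that level and escalation.

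Much of this stands. The practical risk is probably small, the severe row is stricter after the vote, and reading the moderate row as a full hold relies on its plain words. It does not close the gap, however. The safeguards either leave the decision to judgement or only fix the order of procedures; none requires a hold. A hold on the whole cohort does not conflict with the absence of individual rules.

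A second objection also has force: with no deadline for the DLRM, a full hold need not be short, and late doses could disturb the titration schedule that Part C is meant to test.

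**Conclusion.** The concern holds, as a point to clarify. Followed literally, the rule gives a narrower immediate hold for the worse event, and on neither reading does it hold the affected subject's next dose. The gap lies in the mandatory action before the DLRT recommendation and the sponsor's decision, not in the ability to stop.

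It bears mainly on the 2 of 3 (cohort 12) and 4 of 5 (cohort 13) repeat doses given weekly, in cohorts of up to 6 subjects each. Those are scheduled doses. The number exposed to the gap cannot be derived from the documents, and Sections 2.2.2.4 and 4.3 describe no severe event so far. In Part B the 28-day gaps leave more time for the DLRM to act.

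The conclusion rests on the plain meaning of the two rows. The emphasis on Part C is an inference from the 7-day gaps, the absence of scheduled contact within them, and the missing DLRM deadline. No sample size, endpoint or analysis is affected.

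**What to change.** Reword the first action in the severe row along these lines: *Stop all dosing in the cohort, first and repeat doses alike and including the affected subject, and convene a DLRM.* This settles both readings and brings the row into line with the unlimited hold the sponsor already accepts for moderate events.

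The cost is one line in Table 11 and a note to the 1 to 3 sites (Section 4.2.2). When the rule is triggered, scheduled doses in the cohort may be delayed until the DLRM has met, and since no deadline is stated the delay may not be short. If a cohort-wide pause is thought too disruptive to the Part C schedule, an explicit hold limited to the affected subject's next dose would still meet the core of the concern.
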